13.2. Sample size/ power analyses

Power calculations were estimated using Mplus by creating a Monte Carlo Simulation by generating a synthetic data set based on the expected parameter values, such as slopes, standard errors, and correlations among measured variables, for the anticipated treatment effect.^{113,114} Power was estimated assuming an intracluster correlation of 0.5, which is similar to our previous NIDA-funded studies.^{105,112,115} Statistical tests were two-sided, allowing detection of effects in either direction, and an alpha of .05 and power at 80%, corresponding to moderate effect sizes. Because the outcome is a count (i.e., Poisson), standard errors were estimated as non-normal via a sandwich estimator in Mplus.¹¹⁶ Co-Is [name] and [name] found that the number of participants who initiated people into injection was halved at follow-up.⁷ Preliminary data from MPIs [name] and [name]'s study in LA and SF indicated that 809 active PWID were found to have initiated 431 people in the past year. Using the same proportion, we expect that 573 people would be initiated by our proposed sample size of 1,076 participants at baseline (286 in each arm). If the number of people initiated by intervention group participants is halved, as suggested by [name] and [name]'s pilot data, that would represent a reduction of 143 people not being initiated into injection.

We also calculated the effect under different assumptions of attrition, subgroups (e.g., 25% Latino), sex, and age. For brevity, we illustrate power for primary outcome and most conservative—changes in the number of injection initiation events. We also account for 25% attrition—our worst-case scenario. To test the three hypotheses given our alpha and power specifications, we would need a baseline recruitment of 1,076 (n=538 per condition). We will recruit 1,076 participants to achieve the final sample of approximately 800 at the 12-month data point. The sample power for Cohen's effect sizes for small (2 percentage point difference), medium (5% difference) and large (10%–15% difference) effect sizes are plotted in **Figure 4**, revealing that after

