accounting for attrition, a final study of 800 participants at the 12month follow-up, evenly randomized, will have excellent power to detect small (0.82), moderate (0.88), and large (0.99) effect sizes. We also examined power for our mediational analyses in which the injection initiation risk variables will be differentially associated with treatment assignment. Following data from Co-I [name] for the mediational models, we expect that there was a 37% change in transition from initiation to non-initiation, and a 38% reduction in the participants injecting in front of injectionnaive people. These parameter estimates were converted to a Monte-Carlo simulation in Mplus, and we will have power to detect a mediational effect of for moderate to large pathways (Tx \rightarrow Mediator \rightarrow Outcome). Note that we will not have sufficient power for small mediational effects with our proposed sample, which may be clinically insignificant anyway.

1000

1500

High

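### The powers stated for small, medium and large effects (0.82, 0.88, 0.99) cannot all hold at one control rate, and the claim for a 2-point difference is unsupported

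*Combined protocol and SAP*

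**What the plan says.** All of this is in section 13.2. The effect sizes are labelled Cohen's and described as "small (2 percentage point difference), medium (5% difference) and large", the large effect being 10–15%. The sample is "a final study of 800 participants at the 12month follow-up, evenly randomized", that is 400 per arm, and the section says that it "will have excellent power to detect small (0.82), moderate (0.88), and large (0.99) effect sizes". On the error rate: "Statistical tests were two-sided, allowing detection of effects in either direction, and an alpha of .05". The specification is "power at 80%, corresponding to moderate effect sizes".

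The outcome illustrated is "changes in the number of injection initiation events", which is a count. The expected effect comes from the pilot, where "the number of participants who initiated people into injection was halved at follow-up". The only baseline figure is also on the count scale: 431 people initiated in a year by 809 people who inject drugs. "Power was estimated assuming an intracluster correlation of 0.5", with no statement of what forms a cluster. The method was a Monte Carlo simulation in Mplus. Its parameter values are not listed, and neither is a control-arm proportion. The powers are said to be plotted in Figure 4, which is not in the copy reviewed.

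**The concern.** When the sample size is fixed, power climbs steeply with effect size. An effect 2.5 times as large should not move power only from 0.82 to 0.88. A 2-point difference is also very small for a trial with 400 per arm, so 0.82 is surprising in itself. The section disagrees with itself on two further points: it ties 80% power to moderate effects but reports 0.82 for small ones, and it expresses effects in percentage points while saying that the power shown is for a count.

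These are the only numerical power results given for the primary outcome; the 80% is a specification, and no power is given for the pilot's halving. A reader who relied on the text would take a null result as good evidence against a 2-point effect. If the claim is wrong, that reading is wrong too.

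**Working it through.** **Inputs.** From section 13.2: two-sided alpha 0.05 (critical value 1.960), n = 400 per arm, effects of 2, 5 and 10–15 points, stated powers 0.82, 0.88 and 0.99. The control proportion is not stated, so 5% to 50% is assumed.

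**Formula.** SE = √{[p₁(1−p₁) + p₂(1−p₂)]/n}; λ = |p₁−p₂|/SE; power = Φ(λ−1.960) + Φ(−λ−1.960). Using a pooled variance changes power by at most 0.005.

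**1. Can each stated figure be reproduced?** Yes, but each at a different base rate.
- 2% v 0%: SE = √(0.0196/400) = 0.0070, λ = 2.86, power about 0.81.
- 8% v 3%: SE = √[(0.0736 + 0.0291)/400] = 0.0160, λ = 3.12, power 0.88.
- 20% v 10%: SE = √[(0.16 + 0.09)/400] = 0.025, λ = 4.00, power 0.98.

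A control rate of 2% cannot fall by 5 or 10 points, so these cannot describe one trial.

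**2. What λ do the stated powers require?** λ = 1.960 + z(power).
- 0.82: 1.960 + 0.915 = 2.875
- 0.88: 1.960 + 1.175 = 3.135
- 0.99: 1.960 + 2.326 = 4.286

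The ratio is 1 : 1.09 : 1.49, against effects of 1 : 2.5 : 5–7.5. With a common SE, 0.82 at 2 points gives λ = 2.875 × 2.5 = 7.19 at 5 points, a power above 0.999. Conversely, 0.88 at 5 points gives λ = 3.135 × 0.4 = 1.254 at 2 points, a power of 0.24. To reconcile the two, the SE would have to grow by 2.5/1.09 = 2.3 times between the two effects at the same sample size.

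**3. Does any base rate and sample size give both?** The control rate was scanned over 0–100% and n from 50 to about 12,000 per arm. No combination gave 0.82 at 2 points and 0.88 at 5 points, each within 0.02. Wherever 2-point power lay between 0.80 and 0.84, 5-point power was at least 0.997.

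**4. Power for a 2-point reduction, 400 per arm.** The second row credits a baseline-adjusted mean of two follow-ups, reading the 0.5 as correlation between waves: variance factor = (1 + 0.5)/2 − 0.5² = 0.5.

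| Control rate | 5% | 10% | 20% | 30% | 50% |
|---|---|---|---|---|---|
| Simple test | 0.30 | 0.17 | 0.11 | 0.10 | 0.09 |
| Variance halved | 0.53 | 0.29 | 0.17 | 0.14 | 0.13 |

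A simulation of three correlated binary waves (4,000 replicates, sandwich SE) gave 0.53, 0.29, 0.17, 0.15 and 0.13 for the second row. At low rates, even with the variance halved, 0.82 is reached only near 3% v 1%, where no 5-point reduction is possible. For power 0.82 at 2 points, n per arm = 2.875² × [p₁(1−p₁) + p₂(1−p₂)]/0.02². That is 1,583 at a 5% and 6,358 at a 20% control rate, or 792 and 3,179 with the variance halved.

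**5. Other readings.**
- Standardised effects: λ = d√(n/2). For d = 0.2, λ = 2.83 and power is 0.81, close to 0.82. For d = 0.5, λ = 7.07 and power is 1.00, not 0.88.
- Counts: 431/809 = 0.533 a year, or 0.266 per 6 months if spread evenly (an assumption). An absolute difference of 0.02 from either rate has power below 0.09 under Poisson variance.
- Relative changes in the count of 5% or 15%: about 0.08 or less, and at most about 0.36.

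**6. What the sample can detect.** The difference detectable with 80% power from 10%, 20% or 50% is 5.2, 7.3 or 9.8 points (3.8, 5.3 or 7.0 with the variance halved). Halving the proportion who initiate has simple-test power 0.77 at a 10% and 0.98 at a 20% control rate. Halving the count from 0.266 has power 0.99, 0.85 or 0.56 with Poisson variance inflated 1, 2 or 4 times.

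**The case against.** The strongest reply is that the comparison is not the planned analysis. The primary outcome is a count in a two-part zero-inflated Poisson growth model, and the powers came from simulating it, whereas most of the checks above use proportions. Figure 4, which could not be seen, may show a base rate or scale. Only the small effect is explicitly in percentage points. And the simulation was built for the anticipated effect, the halving, so the 2-point figure may never have been the planning target.

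Some of this stands. The simulation cannot be replicated, and the planned model's exact power is unknown. A control proportion is missing, but a count rate is given. The low-rate solutions in steps 1 and 4 have mirror images at rates near 100%, which are implausible for this outcome. That 0.82 came from d = 0.2 is only a guess. The undefined intracluster correlation is a reporting gap, not an arithmetic error.

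None of it rescues the three figures. The ratio check needs no base rate and no particular model, only an SE that does not more than double between the small and medium effects. A label in Figure 4 could not reconcile powers that fit no single base, and the relative reading lowers them further. That the sample may suit the halving is a reason to report that power, not to leave the 2-point claim in place.

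**Conclusion.** The concern holds. The three stated powers are mutually inconsistent for the effects to which they are attached. More than 80% power for a 2-point difference is not supported at any control rate examined between 5% and 50%: the figure is 0.30 to 0.09 in a simple test, and 0.53 to 0.13 with the variance halved. The 0.99 for large effects is plausible on its own at control rates of roughly 10% to 21% for 10 points.

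The power figures rest on a normal approximation, 400 per arm and an assumed control proportion; the ratio argument does not need the last of these. The conclusion concerns the stated powers. It does not show that 1,076 participants are too few for the pilot's halving, where power depends on the control rate and on overdispersion. The text must be corrected because it claims a property that the design has not been shown to have.

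**What to change.** Keep N = 1,076 and revise section 13.2 as follows.

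1. State one assumed control proportion or mean count for the 6-month recall period, with its source. The 431/809 figure is available, but it covers a year, so the conversion must be stated.
2. Say whether effects are percentage points, counts or standardised differences.
3. From that single base, at 400 per arm, report power for each effect, the difference detectable with 80% power, and power for the pilot's halving. List the simulation inputs, including zero-inflation and overdispersion.
4. State what the intracluster correlation of 0.5 refers to.
5. Withdraw the claim of excellent power for a 2-point difference, reconcile the remark linking 80% power to moderate effects, and bring Figure 4 into line.

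To show the format only, with an assumed 20% control rate and a simple test: power 0.11, 0.46 and 0.98 for 2, 5 and 10 points; 7.3 points detectable with 80% power; 0.98 for the halving. The published figures should come from the planned model.

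The cost is a rerun of the power simulation, or a rebuild if the code is lost, and revised wording. No participants are added, and design and analysis do not change. The stated power will look less favourable.

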13.3 Missing data

The likelihood of missing data at the item level will be reduced by using CAPI. Therefore, much of the missing data will likely be due to participant-attrition. We will attempt to gather detailed tracking information to mitigate the likelihood of dropout, which has been approximately 25% at 12 months in our prior NIDA-funded studies of this population in LA and SF. We will censor data at the point of loss to follow-up. Other options, such as last-observation carried forward, will also be explored. As the team has done in previous studies, separate intent to treat (ITT) analyses will be conducted by treating the dropouts as the unfavorable outcome. We will explore mechanism of attrition, and can explore model-based extrapolations, such as pattern mixture modeling to account for data that are non-missing at random and the selection mechanism cannot be explained by observed covariates.^{103,117-119} Regardless of the method used to redress missing data, we will

0.2

0

0

500

conduct sensitivity analyses by comparing results using these procedures to those that exclude missing data altogether so that reviewers may incorporate any differences in the evaluation of our work.

13.4. Elucidation Study 1

We will use descriptive statistics to characterize participants responses to these items.

13.5. Elucidation Study 2

Interviews and data analysis will be conducted by experienced qualitative interviewers (Drs. [name], [name], [name]). We anticipate qualitative interviews taking no more than 60 minutes. All interviews will be audio-recorded. Participants will receive \$10 for completing the interview. The interviews will be digitally recorded and later transcribed verbatim by a professional transcription service that the investigative team has worked with successfully for four years. Transfer of audio files is accomplished through Hightail website. Audio files on digital recorders are erased after been transferred to [name] password protected computer. Thematic analysis of transcriptions will be coded and read to determine if new questions need to be added to explore emerging themes. This iterative analytic meeting will occur every other week until all 40 interviews are completed or therotical saturation has been achieved. Coding of interviews involves reading transcripts in their entirety, coding them and meeting with the research team to refine codes and check for inter-coder reliability. Coding will be conducted using Atlas-Ti qualitative data analysis software.

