2.0 OBJECTIVES AND PURPOSE

To achieve these aims, people who inject drugs (PWID) who report having initiated someone or having injection initiation social learning risks in the past 6 months (N=1,076) will be randomly assigned to receive CTC or an equal attention control condition in Los Angeles (LA) and San Francisco (SF), CA. Injection initiation

and injection initiation social learning variables will be collected at baseline, 6 months, and 12 months. CTC is brief, easy to implement, and novel in its focus on active PWID as a conduit for preventing injection initiation. If proven efficacious, CTC will be a much-needed, practical approach to preventing drug injection initiation.³⁹⁻⁴³

The main outcomes by Aim are as follows: 1) Counts of non-injectors initiated into drug injection at 6 and 12 months; 2) Counts of request to initiate a non-injector into drug injection at 6 and 12 months; and 3) Counts of noninjectors initiated into drug injection and request to initiate non-injectors at 6 and 12 months. The study will be implemented in 2 phases. Phase 1 involves adaptation and training of intervention personnel and Phase 2 involves implementing the full study.

Elucidation goals are to better understand issues related to 1) HAV/HCV effects and 2) drug effects and withdrawal and symptoms management PWID.

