Aim 1: To test the efficacy of CTC on reducing the number of non-injectors initiated into injection (counts) by PWID. Hypothesis 1(H1): PWID who receive CTC will report initiating fewer non-injectors into drug injection at 6 and 12 months as compared with PWID in the equal attention control condition. To test H1, we will conduct structural equation modeling (SEM) using Mplus (release 7.11).99 Our primary outcome analysis is based on an outcome that is distributed as counts of the number of episodes initiating someone into drug injection. This is a standard Poisson count variable with a potential inflation of the number of zeros as there will likely be many who do not initiate others (e.g., zero-inflation). This Poisson count outcome can essentially be thought of as consisting of two separate, yet interrelated, processes-one in which the participant engaged in the behavior of initiating someone else at all (i.e., binary yes/no) and another in which we assess the number of times the participant initiated someone (ranging from 1 to j, where j=the number of episodes initiating someone. In SEM literature, this is referred to as a two-part process for zero inflated Poisson, as SEM models these two processes separately as unique latent processes.¹⁰⁰ As this outcome is collected as part of an intervention with a baseline (T0) and two follow-ups (T1, T2), the model is parameterized to accommodate three time points, following Olsen and Schafer (2001).¹⁰⁰ Note that with three time points, the implied model is mis-identified given the number of measured variables in the variance-covariance from the observed data in an SEM measurement model with an intercept (i) and slope (s) for 3 observations.¹⁰¹⁻¹⁰³ However, joint modeling the ZIP as a two-part process redresses the identification problem, and results in 6 measured variables, one for the process in which the participant actually initiated another person (0 for no, 1 for yes) and another for the

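### The ITT analysis gives dropouts an unfavourable value that is undefined for a count; if they are scored as initiators, the result is diluted and unequal loss appears as a treatment effect

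*Combined protocol and SAP*

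**What the plan says.** Section 13.1 (Aim 1) defines the endpoint: "Our primary outcome analysis is based on an outcome that is distributed as counts of the number of episodes initiating someone into drug injection". It is modelled in two parts, whether the participant initiated anyone and, if so, how many people. Section 3.16 asks for the number over the past 6 months, and Aim 2 is handled the same way for requests.

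Section 13.3 expects most missing data to come from attrition, "which has been approximately 25% at 12 months in our prior NIDA-funded studies of this population in LA and SF". It commits to the following: "separate intent to treat (ITT) analyses will be conducted by treating the dropouts as the unfavorable outcome". No other part of the plan's text uses the term intention to treat.

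The same section censors data at loss to follow-up and adds: "Other options, such as last-observation carried forward, will also be explored". It allows for pattern-mixture models and promises that results under any method will be set beside results that exclude missing data. Section 13.1 plans a test for differential loss between conditions.

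Section 13.2 sizes the trial with the same attrition ("We also account for 25% attrition") to "achieve the final sample of approximately 800 at the 12-month data point".

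**The concern.** An unfavourable outcome is easy to assign to a binary endpoint. A count running from zero to no stated maximum has no obvious worst value, and the plan does not supply one. The analyst would have to choose it, or choose which part of the model receives it, after data collection.

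The natural reading is to score each dropout *yes* on initiating someone. Everyone lost then becomes an initiator, although Section 13.1 expects many zeros. Two consequences follow. A true effect is diluted, because the same block of assumed events is added to both arms. And if the arms lose different proportions, the difference in retention is itself counted as outcome.

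Unequal loss is plausible. Under Section 5.3, participants who cannot complete their assigned session may be asked to withdraw. That happens after randomisation, and the two sessions differ in content.

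**Working it through.** **Inputs from the documents.** 538 per arm, 25% loss at 12 months, two-sided alpha of 0.05, and a halving of initiation as the anticipated effect (Sections 13.2 and 13.3). Background rate: 431 people initiated by 809 participants in a year (Section 13.2).

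**Inputs assumed.** The documents do not give the proportion of participants who initiate anyone, so control rates of 10% to 30% are used. Loss of 28% v 22% is an illustration with a mean of 25%.

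**The plan's own figures reproduce.** 431/809 × 1,076 = 573; 431/809 × 538 = 286.6 per arm (stated as 286); half of that is 143. Retained: 1,076 × 0.75 = 807, stated as about 800.

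**Numbers lost and observed.** Lost per arm: 538 × 0.25 = 134.5. Observed: 403.5. The lost outnumber observed initiators when the proportion initiating among those observed is below 134.5/403.5 = 33.3%.
- Halving the annual rate to 6 months (an assumption) gives 0.533/2 = 0.266 people per participant. At one person per initiator, the maximum number of observed control initiators is 403.5 × 0.266 = 107; with a halving on CTC it is 54. Both are below 134.5.
- Applying the annual rate unscaled to one 6-month window gives up to 403.5 × 0.533 = 215 control initiators. The lost then outnumber them only if initiators average more than 215/134.5 = 1.6 people each.

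**Equal loss.** With loss d, the scored proportion is d + (1 − d)p, so the difference becomes (1 − d)(p_C − p_T), which is 0.75 of its true size. Power is for a two-proportion test: Φ[(Δ − 1.96·SE₀)/SE₁], where SE₀ is the pooled and SE₁ the unpooled standard error. It uses 403.5 observed per arm, or 538 per arm with dropouts scored *yes*.

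| True control v CTC | Power, observed only | Scored control v CTC | Power, dropouts scored *yes* |
|---|---|---|---|
| 10% v 5% | 77% | 32.5% v 28.75% | 27% |
| 15% v 7.5% | 92% | 36.25% v 30.6% | 50% |
| 20% v 10% | 98% | 40.0% v 32.5% | 73% |
| 30% v 15% | over 99% | 47.5% v 36.25% | 96% |

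For the 15% row, Δ = 0.0563, SE₀ = 0.0288 and SE₁ = 0.0287, so Φ(−0.004) ≈ 0.50. The risk ratio moves from 0.50 to 30.6/36.25 = 0.84, and 25/36.25 = 69% of the scored control initiators are imputed.

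**Unequal loss, no true effect.** With 28% lost on CTC and 22% on control, the artefact is (0.28 − 0.22)(1 − p) = 0.06(1 − p).
- p = 10%: 35.2% v 29.8%, 5.4 points against CTC, rejection in 47% of trials.
- p = 30%: 49.6% v 45.4%, 4.2 points against CTC, rejection in 28% of trials.

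Section 13.2 calls a 5% difference a medium effect.

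**Unequal loss that erases a true halving** (mean loss 25%). The excess CTC loss needed is 0.75(p_C − p_T)/[1 − (p_C + p_T)/2]. At 10% v 5% this is 0.0375/0.925 = 4.1 points; at 30% v 15% it is 0.1125/0.775 = 14.5 points.

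**The case against.** The strongest reply is that this is one separate analysis. Hypothesis 1 is tested in the two-part zero-inflated model, and Section 13.3 sets every missing-data method beside results that exclude missing data, so a reader would see any discrepancy. Worst-case scoring is also meant to be conservative, and with equal loss it keeps the direction of effect. All of this stands. A reader might infer that attrition decides the trial's result; the documents do not support that.

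Three other strong readings also fail.
- *A count can have no unfavourable value.* The yes/no item in Section 3.16 and the binary part of the model do have one. The gap is that the plan does not say the rule is confined to that part.
- *The lost are bound to outnumber observed initiators.* This depends on a proportion that the documents do not give. Entry is limited to people "who report having initiated someone or having injection initiation social learning risks in the past 6 months (N=1,076"), which could raise it above the 0.533 annual rate's implications, and the 25% is a 12-month figure with no 6-month counterpart.
- *Last observation carried forward always inserts a high baseline count.* Entry by social-learning risk alone allows a baseline count of zero, and people lost after 6 months would carry a 6-month value. The plan only says the method will be explored.

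The planned test of differential loss helps only in part. At 538 per arm it would flag 28% v 22% about 62% of the time. Flagging does not repair an analysis in which loss is itself the outcome, and neither does covariate adjustment. Nor does the side-by-side comparison say which result governs when the two disagree. Conservatism is no defence against unequal loss, since heavier loss on control would favour CTC.

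**Conclusion.** The point holds for the analysis named as intention to treat. Its dropout value is undefined for the counts, so it cannot be run on them as written.

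If dropouts are scored as initiators, equal 25% loss removes a quarter of the risk difference. The power cost for a true halving is severe at low initiator rates (77% to 27% at 10%) and small at high ones (over 99% to 96% at 30%). Imputed cases exceed observed initiators in any arm where fewer than 33.3% of those observed initiate. That is so if the plan's annual rate is halved to 6 months, but it is not established by the documents.

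A six-point difference in loss with no true effect gives 28% to 47% rejection over control rates of 30% down to 10%. These sizes rest on the assumed rates and the assumed loss pattern. The primary model-based test is not affected.

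**What to change.** Replace the sentence on separate ITT analyses in Section 13.3 with wording such as:

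*The ITT analysis includes all randomised participants in their assigned arm, on the count scale. Missing 6- and 12-month counts are handled by likelihood-based estimation or by multiple imputation from arm, site, baseline count and any observed follow-up count. A sensitivity analysis multiplies imputed counts by a range of factors (for example 1 to 3), set separately by arm, and reports the factors at which the conclusion changes.*

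In practice the factor should act on the expected count before it is drawn, because a drawn zero stays zero under any multiplier.

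Keep dropout-as-initiator as one labelled extreme, applied to the yes/no part only. Do not rely on last observation carried forward: for anyone lost before 6 months it substitutes a pre-randomisation value for follow-up.

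The cost is SAP wording and some analyst time. The simple worst-case figure used in the team's earlier studies would no longer be the named ITT result.

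### The complete-case comparison attached to every missing-data method says little about outcome-dependent dropout, and no committed, defined analysis varies the dropout assumption by arm for the count outcomes

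*Combined protocol and SAP*

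**What the plan says.** Section 13.3 expects most missing data to come from attrition, "which has been approximately 25% at 12 months in our prior NIDA-funded studies of this population in LA and SF". Section 13.2 plans for the same figure: "We also account for 25% attrition—our worst-case scenario".

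Section 13.3 names several ways of handling dropout, with different degrees of commitment:

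- Data are censored at the point of loss (the default).
- Last observation carried forward will be explored.
- Separate intention-to-treat analyses, scoring dropouts as unfavourable, are a firm commitment.
- For missingness that observed covariates cannot explain, the team "can explore model-based extrapolations, such as pattern mixture modeling to account for data that are non-missing at random". This is optional, and no assumptions or shift values are given.

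Whichever method is used, the team will "conduct sensitivity analyses by comparing results using these procedures to those that exclude missing data altogether so that reviewers may incorporate any differences". This is the only check labelled a sensitivity analysis and the only one tied to every method. The section sets no rule for what would count as robust.

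Section 13.1 adds a test for differential loss between conditions. Variables associated with that loss become covariates.

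**The concern.** The censored-data model and the complete-case analysis both draw on counts that were reported, and neither sees the counts of people who did not return. If non-return depends on those counts in one arm only, both estimates move the same way, and setting one beside the other does not expose the shift.

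Arm-specific non-return is plausible here. The outcome is a self-report, made face to face to an interviewer (Sections 3.13 and 3.16), of having helped someone inject for the first time. Only CTC participants discuss the risks of initiating others and rehearse avoiding it (Section 7.1.1). A CTC participant who later initiates someone may therefore have a reason to stay away that a control participant lacks. The documents do not show that this will happen, but the plan should be able to test how much it would matter. What is at stake is a false CTC effect on H1 or H2 that could look robust.

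**Working it through.** **Inputs from the documents.** 1,076 randomised, 538 per arm; 25% loss; about 800 at month 12; two-sided alpha 0.05, so 2.5% in favour of CTC; 431 people initiated by 809 PWID in a year (Section 13.2).

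**The plan's own figure.** 1,076 × (1 − 0.25) = 807, which agrees with about 800. About 269 outcomes would be missing.

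**Event rate.** 431/809 = 0.533 per person-year, or 0.266 per six months if constant.

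**Assumptions not in the documents.** Person-to-person variation is gamma with shape 0.3, so the proportion initiating in six months is p = 1 − (0.3/(0.3 + 0.266))^0.3 = 0.17. Sixty per cent of dropouts leave before month 6. Loss rates by arm and initiator status are as tabled. A Poisson GEE on all available data stands in for the two-part model.

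**Simulation.** 600 trials per scenario with no true effect. Cells give the rate ratio (risk difference in the last column) and the percentage of trials falsely favouring CTC.

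| Loss, initiators / non-initiators | Available data | Complete case | LOCF | Dropout scored as initiator (yes/no) |
|---|---|---|---|---|
| (a) both arms 25/25 | 1.00, 2% | 1.00, 2% | 0.99, 2% | 0.00, 3% |
| (b) both arms 40/22 | 1.00, 3% | 1.00, 2% | 1.00, 2% | 0.00, 2% |
| (c) CTC 50/20, control 25/25 | 0.73, 41% | 0.66, 49% | 0.87, 13% | −0.04, 28% |
| (d) CTC 50/25, control 25/25 | 0.77, 32% | 0.70, 38% | 0.89, 11% | 0.00, 3% |

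Total loss is equal by arm in (c), at about 25%. In (d) it is 29% against 25%. Monte Carlo error at 41% is √(0.41 × 0.59/600) = 2 points.

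**Hand check, complete case.** Under no effect, RR = (1 − loss in CTC initiators)/(1 − total CTC loss).
- (c): total loss 0.17 × 0.50 + 0.83 × 0.20 = 0.25; RR = 0.50/0.75 = 0.67.
- (d): total loss 0.17 × 0.50 + 0.83 × 0.25 = 0.29; RR = 0.50/0.71 = 0.70.

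**Hand check, dropouts as unfavourable.** P(unfavourable) = p + (1 − p)q, where q is loss among non-initiators; loss among initiators cancels.
- (c): difference = 0.83 × (0.20 − 0.25) = −0.04.
- (d): difference = 0.83 × (0.25 − 0.25) = 0.

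**Cost of that rule when CTC truly halves the rate** (25% loss in both arms, unrelated to outcome). The proportion initiating falls from 0.174 to 0.104.
- Scoring dropouts as initiators gives 0.174 + 0.826 × 0.25 = 0.380 against 0.104 + 0.896 × 0.25 = 0.328, a difference of 0.052. SE = √(0.380 × 0.620/538 + 0.328 × 0.672/538) = 0.029; z = 1.78; power = Φ(1.78 − 1.96) = 0.43 (simulated: about 44%).
- The same yes/no outcome in month-12 completers (403.5 per arm): difference 0.069, SE 0.024, z = 2.86, power = Φ(0.90) = 0.81.
- The count in month-12 completers: simulated power 92%.

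So part of the loss comes from reducing the count to yes/no, and most comes from dilution.

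**How close the two observed-data analyses come.** On the log scale they differ by 0.414 − 0.313 = 0.10 in (c) and 0.353 − 0.266 = 0.09 in (d). A second simulation used a random-intercept Poisson model, log-normal variation with SD 1.3, 10% random loss at month 6 and 25% total loss in both arms. With CTC loss of 45% in initiators and 21% in others, it gave 0.77 against 0.77, with two-sided false-positive rates of about 32% and 29%. The log-scale gap across its scenarios was 0.003 to 0.02. The size of the gap depends on the assumptions; the shared direction does not.

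**What a shift analysis would show.** With 25% loss and CTC dropouts at δ times the observed CTC rate, adjusted RR = RR × (0.75 + 0.25δ). It reaches 1 at δ = (1/RR − 0.75)/0.25:
- RR 0.77: (1.299 − 0.75)/0.25 = 2.2
- RR 0.73: (1.370 − 0.75)/0.25 = 2.5
- RR 0.66: (1.515 − 0.75)/0.25 = 3.1

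Statistical significance would be lost at a smaller δ.

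**The case against.** The strongest reply is that Section 13.3 does more than complete-case. It firmly commits to an intention-to-treat analysis scoring dropouts as unfavourable, which is itself a not-missing-at-random analysis. The complete-case comparison applies to that analysis too, so readers will see two results that can diverge sharply. If only CTC initiators stay away more, as in (d), that analysis is unbiased for the yes/no outcome. Scenario (c) needs CTC non-initiators to be retained better than controls, for which there is no obvious reason.

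Much of this stands. A reader might infer that complete-case is the plan's only alternative analysis, or that pattern mixture is its only tool for informative dropout; the commitment above rules out both. A reader might also infer that a false effect would look robust. The documents give no evidence of arm-specific dropout, and (b) shows no bias in the comparison when the pattern is shared, so the word is could. Nor are the two biases the same: they are similar, with a gap that varies with the assumptions. Finally, the plan offers the comparison for readers to weigh and does not say that agreement proves robustness.

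The unfavourable-outcome analysis still leaves a gap. It is one extreme assumption for both arms. H1 and H2 concern counts, and no unfavourable count is defined. With equal total loss, as in (c), it still favours CTC falsely in 28% of trials, and the test for differential loss in Section 13.1 has no overall difference to find. Because it also dilutes a true effect, its disagreement with the main result cannot separate dropout bias from dilution.

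**Conclusion.** The concern holds in a limited form. Agreement between the censored-data model and the complete-case analysis is close to uninformative about dropout that depends on unseen counts. Under arm-specific dropout of the size in (c) and (d), with no true effect, both favour CTC: rate ratios 0.66 to 0.77, and false CTC findings in 32% to 49% of trials against 2.5%. No defined, committed analysis for the H1 and H2 counts varies the dropout assumption by arm.

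These sizes rest on assumed loss rates by initiator status, assumed person-to-person variation, and a GEE in place of the two-part model. A likelihood model also relies on missing at random, so the direction should carry over, but the size may not. This is a change the plan should make; it does not show that the planned analysis will be biased.

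**What to change.** In Section 13.3, commit to a delta-adjusted (pattern-mixture) multiple imputation for H1 and H2:

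- Impute the missing 6- and 12-month counts by arm from the observed data.
- Multiply the imputed rate in CTC dropouts over a pre-stated range, for example 1, 1.5, 2 and 3, with control dropouts held at 1. Repeat with both arms shifted.
- Report the multiplier at which the CTC conclusion changes.

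Keep the unfavourable-outcome analysis for the yes/no part and state the value assigned to dropouts. Keep complete-case results as description, and do not present them as evidence of robustness to outcome-dependent dropout.

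The cost is SAP wording and a few extra runs on data already being collected. The downside is that a significant result may be shown to depend on a modest departure among dropouts.
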